9.4.2 Clinical Laboratory

For the treatment-emergent laboratory assessments, the observed values and change from baseline values of the continuous hematology, coagulation and chemistry results will be summarized in SI units at each visit by treatment group.

The number and percentage of subjects meeting at least 1 threshold analysis criterion event, during the TE period for Treatment Period, will be summarized by treatment group. The threshold analysis criterion shift from baseline will also be summarized for selected laboratory parameters. The threshold analysis criteria are provided in [Appendix F](#).

For selected LFT laboratory test (alanine transaminase [ALT], aspartate transaminase [AST], alkaline phosphatase [ALP], and total bilirubin), a scatter plot of the maximum treatment-emergent value versus the baseline value corresponding to \times ULN (upper limit of normal) will be presented. Further, a scatter plot of the maximum treatment-emergent value of ALT and AST,

separately, versus the maximum treatment-emergent value of total bilirubin corresponding to \times ULN will also be presented by treatment group.

Results of positive urine/serum pregnancy test will be listed in individual subject data listings only. For positive serum pregnancy listing, subjects with serum HCG which are abnormally high will be selected.

In addition, a listing containing individual subject hematology, chemistry, coagulation and urinalysis values will be provided. This listing will include data from both scheduled and unscheduled visits.

9.4.3 Electrocardiogram

For the treatment-emergent ECG measurements, a summary of observed values and change from baseline values will be provided at each visit by treatment group for the following ECG interval measurements (in msec): RR interval, PR interval, QT interval, QTcF interval, QRS duration, and Heart Rate (beats per minute).

The number and percentage of subjects meeting at least 1 threshold analysis criterion during the TE period for the Treatment Period will be summarized by treatment group. The threshold analysis criteria are provided in [Appendix F](#).

In addition, a listing containing individual subject ECG values will be provided. This listing will include data from both scheduled and unscheduled visits.

9.4.4 Vital Signs

For the treatment-emergent vital signs measurements, the observed values and change from baseline values will be summarized at each visit by treatment group. The following vital signs parameters will be summarized: systolic and diastolic blood pressure (mm Hg), body temperature ($^{\circ}$ C), pulse rate (beats per minute), and respiratory rate (breaths per minute).

The number and percentage of subjects meeting at least 1 threshold analysis criterion during the TE period for the Treatment Period will be summarized by treatment group. The threshold analysis criteria are provided in [Appendix F](#).

In addition, a listing containing individual subject vital signs values will be provided. This listing will include data from both scheduled and unscheduled visits.

9.4.5 Pulse Oximetry

For the treatment-emergent pulse oximetry measurements, a summary of observed values and change from baseline values will be provided at each visit by treatment group, for the percent of oxygen saturation.

The number and percentage of subjects with shift changes from baseline (normal/missing and low according to the reference range) to the lowest percent of oxygen saturation during the TE period for the Treatment Period will be summarized by treatment group.

9.4.6 Physical Examination

PE findings will be presented as an individual subject data listing only.

9.4.7 Ophthalmology Examination

Ophthalmology examination results will be provided in a data listing.

9.4.8 COVID-19 Impacted Visits

A listing containing subjects' visits impacted due to COVID-19 will be provided.

9.4.9 Supportive Safety Analysis

9.4.9.1 Adverse Events of Special Interest

For this study, elevated transaminase events and rash events, as determined by MedDRA preferred terms in [Appendix G](#), are considered as adverse events of special interest.

For treatment-emergent elevated transaminase events and rash events, the following categories will be summarized by treatment group:

- Subjects with events
- Subjects with events by maximum severity
- Subjects with events leading to treatment discontinuation
- Subjects with events leading to treatment interruption
- Subjects with serious events
- Subjects with related serious events
- Subjects with events leading to death
- Duration of events
- Time-to-onset of first event

In addition, for treatment-emergent rash events, these categories will be summarized for the following subgroups:

- Sex (male, female)
- Female subjects with concomitant hormonal therapy (Yes, No)

9.4.9.2 Hormonal Therapy

The number of subjects who used hormonal therapy concomitantly will be summarized by treatment group based on the Safety Set for the Treatment Period.

10 Interim and DMC Analyses

10.1 Interim Analysis

No interim analysis is planned.

10.2 DMC analysis

The DMC's objectives and operational details are defined in a separate document (DMC Charter) which was finalized before the first subject was screened in the study. The DMC's planned safety reviews of study data are outlined in the DMC Charter and DMC Statistical Analysis Plan.

12 LIST OF APPENDICES

Appendix A: Analysis Visit Windows for Safety and Efficacy Assessment

Table 12-1 Analysis Visit Windows for Safety and Efficacy Assessments

Assessment	Visit ¹	Target Study Day	Analysis Visit Window ^{2,3,4} (in study days)
Safety Assessment			
Serum Chemistry Hematology Standard 12-lead ECG	Day 1 (Baseline)	1	≤1 Pre-dose
	Day 15	15	[1, 22]
	Week 4	29	(22, 43]
	Week 8	57	(43, 71]
	Safety Follow-up	Not applicable	Use nominal visit
Coagulation	Day 1 (Baseline)	1	≤1 Pre-dose
	Week 8	57	[1, 71]
	Safety Follow-up	Not applicable	Use nominal visit
Vital Signs (excluding BMI, Weight, Height)	Day 1 (Baseline)	1	≤1
	Day 15	15	[1,22]
	Week 4	29	(22, 43]
	Week 8	57	(43, 71]
	Safety Follow-up	Not applicable	Use nominal visit
Efficacy Assessment and Pharmacodynamic Assessment			
Spirometry ⁵	Day 1 (Baseline)	1	≤1 Pre-dose
	Day 15	15	(1,22]
	Week 4	29	(22, 43]
	Week 8	57	(43, 71]
	Safety Follow-up	Not applicable	>71
Sweat Chloride	Day 1 (Baseline)	1	≤1 Pre-dose
	Day 15	15	(1,22]
	Week 4	29	(22, 43]
	Week 8	57	(43, 71]
CFQ-R Weight, Height and BMI ⁵	Day 1 (Baseline)	1	≤1
	Day 15	15	(1,22]
	Week 4	29	(22, 43]
	Week 8	57	(43, 71]
	Safety Follow-up	Not applicable	>71
Notes:			
¹ Visit name for analysis purpose is used to report data in tables and figures.			
² The analysis visit windows will be applied using the following rules for both scheduled and unscheduled visits:			
a. If no numerical measurement is available within a visit window, the measurement will be considered missing for the visit.			
b. If there is more than 1 numerical measurement available within a visit window, use the following rules:			
i. The measurement closest to the target day will be used; or			
ii. If there are multiple measurements with the same distance from the target day, the latest measurement will be used. If the latest measurement cannot be determined, then unscheduled visit will be selected.			
³ For measurement collected on the date of first dose of study drug in Treatment Period, if it cannot be determined whether the measurement is before or after the first dose:			
a. Scheduled measurement will be treated as pre-dose observation.			

Table 12-1 Analysis Visit Windows for Safety and Efficacy Assessments

Assessment	Visit ¹	Target Study Day	Analysis Visit Window ^{2,3, 4} (in study days)
b. Unscheduled measurement will be treated as post-dose observation.			
⁴ For safety Assessment, Safety Follow-up analysis visit will be based on nominal Safety Follow-up visit. If a subject doesn't have a nominal Safety Follow-up visit but has an ETT visit with study day >71, then the ETT visit will be mapped into Safety Follow-up analysis visit.			
⁵ For efficacy analysis, if there are multiple assessments >71, then nominal Safety Follow-up visit will be mapped to Safety Follow-up visit. If there is only ETT assessment > 71, the ETT visit will be mapped to the Safety Follow-up visit; else if there are multiple assessments with >71 then select the earliest record.			
Derived Variables:			
1. Age (in years) at first dose date and nominal visit (for demographics, listing and the calculation of [percent] predicted spirometry variables):			
Obtain the age at informed consent (in days) in “yy, mm” format (e.g., 24 years, 6 months) from the Vital Signs (VS) page at the Screening Visit, and add 0.5 month to convert to days.			
Obtain the informed consent date.			
Then age (in years) at first dose or nominal visit = [(first dose date or nominal visit date – informed consent date) in days + age at informed consent (in days)]/365.25.			
2. Age (in months) at nominal visit (for use in calculation of BMI and weight z-score, as applicable):			
Obtain the age at informed consent (in months) in “yy, mm” format (e.g., 24 years, 6 months) from Vital Signs (VS) page at the Screening Visit.			
Obtain the informed consent date.			
Then age (in months) at nominal visit = integer part of {[age at informed consent (in months) + 0.5 + diff (nominal, informed consent date) in months]} + 0.5.			
3. Missing first dose date or last dose date			
If the first dose date is missing, use Day 1 visit date to impute.			
If the last dose date is missing or partial date is reported, the last dose date will be imputed based on, in descending order priority, the Early Treatment Termination (ETT) visit date, last visit date before the Safety Follow-up, or the last study drug administration date from EX SDTM domain, as appropriate. The imputation algorithm will ensure the imputed last dose date does not exceed the study participation end date.			
4. Sweat Chloride:			
Non-missing sweat chloride concentrations from the left arm and right arm with assessment end date/time for a given arm up to 30 minutes after first dose time in treatment period will be considered for baseline.			
5. Electrocardiogram:			
Baseline is defined as the most recent pretreatment measurement before the first dose of study drug in the Treatment Period. If multiple ECG measurements are obtained on the same calendar day during the TE period,			

 ○ For summary purpose, the calculated average ECG will be used as the ECG value on that day; 			

 ○ For threshold analysis purpose, all reported ECG values will be used. 			

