9.1.5 Early Termination of Treatment

If a subject prematurely discontinues study drug treatment, an Early Termination of Treatment (ETT) Visit should be scheduled as soon as possible after the decision to discontinue treatment. Subjects who prematurely discontinue treatment will also be required to complete the Safety Follow-up Visit, approximately 28 days after their last dose of study drug. The assessments performed at the Safety Follow-up Visit are listed in Table 3-2.

If the ETT Visit occurs 3 weeks or later following the last dose of study drug, then the ETT Visit will replace the Safety Follow-up Visit, and a separate Safety Follow-up Visit will not be required.

If a subject withdraws from the study and also withdraws consent or assent, no further assessments will be performed. Vertex may retain and continue to use any data and samples collected before such withdrawal of consent or assent.

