9.1.5.2 Discontinuation During the Treatment Period

Subjects who prematurely discontinue study drug treatment during the Treatment Period will continue to complete all scheduled study visits for assessments following completion of the ETT Visit, as detailed in Table 3-2. These subjects will complete an ETT Visit and Safety Follow-up Visit (as applicable; see Section 9.1.5).

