9 STATISTICAL ANALYSIS

9.1 General Considerations

The Schedule of Assessments is provided in Section 3 of CSP. The precision standards for reporting safety and efficacy variables are provided in an internal Biometrics document that specifies the programming rules including the precision for derived variables.

Continuous variables will be summarized using the following descriptive summary statistics: the number of subjects (n), mean, standard deviation (SD), median, minimum value (min), and maximum value (max).

Categorical variables will be summarized using counts and percentages. Percentages will be presented to 1 decimal place.

Baseline value, unless otherwise specified, is defined as the most recent non-missing measurement (scheduled or unscheduled) collected before the first dose of study drug in the Treatment Period (i.e., the Day 1 Visit). For ECGs, baseline will be defined as the most recent pretreatment measurement before the first dose of study drug in the Treatment Period (i.e., the Day 1 Visit).

Absolute change from baseline will be calculated as post-baseline value - baseline value.

Relative change from baseline will be calculated as (post-baseline value - baseline value)/baseline value.

The **Treatment-emergent (TE) Period for the Run-in Period** will be from the first dose of study drug in the Run-in Period to (1) the first dose of study drug in the Treatment Period for subjects who complete the Run-in Period and continue to the Treatment Period, or (2) 28 days after the last dose date of study drug in the Run-in Period or to the completion of study participation date, whichever occurs first, for subjects who do not continue to the Treatment Period (e.g., subjects who do not meet the conditions to enter the Treatment Period).

The **TE Period for the Treatment Period** will include the time from the first dose date of study drug in the Treatment Period (TC, placebo + TEZ/IVA, or placebo + IVA) to 28 days after the last dose of the study drug or to the completion of study participation date, whichever occurs first.

Unscheduled visits: Unscheduled visit measurements will be included in analysis as follows:

- 1) In scheduled visit windows per specified visit windowing rules
- 2) In the derivation of baseline
- 3) In the derivation of maximum and minimum values during TE period, and maximum and minimum change from baseline values during TE period for safety analyses
- 4) In individual subject data listings as appropriate

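### SAP Appendix A ranks visit dates above the dosing record when it imputes a missing or partial last-dose date, so a few subjects can be credited with exposure they did not have

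*SAP*

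**What the plan says.** SAP Appendix A, Derived Variables item 3, sets both the trigger and the ranking: "If the last dose date is missing or partial date is reported, the last dose date will be imputed based on, in descending order priority". Three sources follow: "the Early Treatment Termination (ETT) visit date, last visit date before the Safety Follow-up, or the last study drug administration date from EX SDTM domain". There is one limit: "The imputation algorithm will ensure the imputed last dose date does not exceed the study participation end date". Nothing requires the result to agree with the part of a partial date that is known, or with EX.

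The date feeds three SAP outputs:
- Exposure duration, its week bands and total patient-weeks (SAP 9.2.5).
- The denominators of compliance and of the percentage of tablets taken (SAP 9.2.6).
- The end of the treatment-emergent (TE) Period, which is the earlier of the two points in "28 days after the last dose of the study drug or to the completion of study participation date" (SAP 9.1).

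Two protocol rules separate visit dates from dosing dates. Subjects who stop drug in the Treatment Period "will continue to complete all scheduled study visits for assessments following completion of the ETT Visit" (Protocol 9.1.5.2). Protocol 9.1.5 also provides for a late ETT Visit, which then stands in for the Safety Follow-up: "If the ETT Visit occurs 3 weeks or later following the last dose of study drug".

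**The concern.** In a trial where dosing and visits end together, a visit date is a fair stand-in for a last dose. Here they are deliberately uncoupled for early stoppers, so the two preferred sources can both fall weeks after dosing ended, while the only source that records dosing is consulted last. Because the rule also covers partial dates, a visit in a later month can override a month and year that the site did report.

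The SAP handles other partial end dates differently. Appendix B keeps a partial medication stop date inside its reported month or year. Appendix E does the same for a partial AE end date and caps it at the end of participation. Study drug is the exception.

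At stake are exposure, tablet percentage and the split between treatment-emergent and post-treatment events in the affected subjects. Some of these will be early discontinuers, for whom event timing matters to the safety reading.

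**Working it through.** The plan states no figure for this rule, so there is none to reproduce. The check applies the plan's own formulas.

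**Inputs**
- Exposure = last dose day − first dose day + 1 (SAP 9.2.5). With first dose on Day 1, this equals the last dose day.
- Exposure bands: ≤2, >2 to ≤4, >4 to ≤8 and >8 weeks (SAP 9.2.5).
- TE end = min(last dose + 28, completion of participation) (SAP 9.1).
- Completion for an early stopper = latest of Week 8, ETT and Safety Follow-up if required; on withdrawal of consent, the withdrawal date (Protocol 9.1.7).
- Safety Follow-up: 28 ± 7 days after the last dose (Protocol Table 3-2).
- Target days: Week 4 = Day 29, Week 8 = Day 57 (SAP Table 12-1).
- Four tablets a day in the Treatment Period: three in the morning, one in the evening (Protocol 9.6.1).

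**Main example: true last dose Day 16, ETT Day 40, Week 8 Day 57**
- The ETT is 40 − 16 = 24 days after the last dose, so it replaces the Safety Follow-up. Completion is Day 57.
- Exposure: 16 days (16/7 = 2.3 weeks, band >2 to ≤4) becomes 40 days (40/7 = 5.7 weeks, band >4 to ≤8).
- Tablets, full adherence: 100 × 64/(4 × 16) = 100% becomes 100 × 64/(4 × 40) = 40%, which falls in the <80% category.
- Compliance moves the other way. With an assumed 5 interruption days, 100 × (1 − 5/16) = 68.75% becomes 100 × (1 − 5/40) = 87.5%.
- TE end: min(16 + 28, 57) = Day 44 becomes min(40 + 28, 57) = Day 57, a gain of 13 days.

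**Other cases** (Week 8 on Day 57)

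| Case | Exposure, true → imputed | TE end, true → imputed |
|---|---|---|
| Stop Day 20, ETT Day 25 | 20 → 25 (+5) | 48 → 53 (+5) |
| Stop Day 16, no ETT date, follow-up on time, so Week 4 is the last visit before it | 16 → 29 (+13) | 44 → 57 (+13) |
| Stop Day 16, no ETT date, follow-up missed, so Week 8 is used | 16 → 57 (+41) | 44 → 57 (+13) |
| Stop Day 40, ETT Day 45, follow-up 28 days after last dose | 40 → 45 (+5) | unchanged |
| Stop Day 20, consent withdrawn at ETT Day 25 | 20 → 25 (+5) | 25 → 25 (0) |
| Completer, last dose evening of Day 56, imputed to Week 8 | 56 → 57 (+1) | unchanged |

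The completer moves from 56/7 = 8.0 weeks (band >4 to ≤8) to 57/7 = 8.1 weeks (band >8).

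**Limit on the TE gain.** It cannot exceed completion − (last dose + 28). With Week 8 on Day 57 and follow-up exactly 28 days after a last dose on Day L, that is max(0, 29 − L): 28 days for L = 1, 19 for L = 10, 9 for L = 20, 1 for L = 28, and zero from L = 29. If follow-up falls at the late edge of its window (35 days), later stops can gain up to 35 − 28 = 7 days.

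**Aggregate, on an assumption.** If 1 to 5 of 125 subjects in an arm were affected by 5 to 37 days each (37 = 57 − 20), mean exposure would rise by 1 × 5/125 = 0.04 to 5 × 37/125 = 1.48 days.

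**The case against.** The best defence has four parts.

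- *Scope.* The rule applies only when the date is missing or partial, and Protocol 9.1.5 wants the ETT Visit as soon as possible after the decision to stop. An ETT three weeks or more after the last dose is the exception. This stands: a reader might infer that early stoppers in general gain exposure, and the documents do not support that.
- *The TE cap.* A reader might infer that the TE Period lengthens day for day with exposure. It does not, because SAP 9.1 also ends it at completion of participation. The gain is 13 days in the main example, where exposure gains 24, and it is zero for stops from about Day 29 with on-time follow-up.
- *Leaning late is cautious.* The SAP elsewhere leans the same way: AEs of unclear timing default to Treatment Period TEAEs (9.4.1), and partial medication stop dates take the latest possible day (Appendix B). For AE capture this has force. It does not make longer exposure or a lower tablet percentage cautious, and Appendix B still stays within the reported month or year.
- *EX may be no better, and judgement is allowed.* Protocol 9.6.1 has individual dose times recorded around PK samples. If EX held only those, putting EX first could date the last dose too early and lose TEAEs. This stands as a condition on the fix. The list's ending, "last visit date before the Safety Follow-up, or the last study drug administration date from EX SDTM domain, as appropriate", leaves some discretion, but the closing words are undefined and do not reverse a stated ranking. By naming EX as a separate source, the SAP itself foresees that EX may hold a date when the last-dose field does not.

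**Conclusion.** The point holds as a minor defect. As written, the rule can produce a last-dose date that contradicts a complete EX record, or a reported month and year when the visit falls in a later month. In the main example the error is 24 days of exposure, a wrong exposure band, 40% instead of 100% of tablets taken, and 13 days of TE time.

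These sizes rest on Week 8 falling on Day 57 and on an ETT 24 days after the last dose. With a prompt ETT they shrink to a few days. The 41-day exposure error needs both no ETT date and no Safety Follow-up before Week 8. The number of affected subjects is unknown, because the documents give no rate of missing or partial last-dose dates.

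Two wider readings should be resisted. A reader might see the same fault in the way Table 12-1 maps a late ETT to the Safety Follow-up row. That note assigns visits to analysis rows and imputes no dose date. A reader might also infer a threat to the efficacy results. The primary and key secondary MMRM analyses use visit-window data and not this date. Safety is descriptive, and AEs are summarised as counts and percentages of subjects, so inflated patient-weeks dilute no planned AE rate.

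**What to change.** Rewrite item 3 of the Derived Variables in SAP Appendix A so that a missing or partial last-dose date is resolved in this order:

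1. A complete last administration date in EX, provided EX records the end of dosing and not only the doses logged around PK samples. The SAP should say which it is.
2. Otherwise, for a partial date, the latest day consistent with the reported month and year, with the ETT or last-visit date as an upper bound.
3. The ETT or last-visit date itself only when nothing else is known.

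Keep the cap at the end of participation, and add a listing of every imputed last-dose date with its source.

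In the main example a complete EX date restores 16 days, 100% of tablets and a TE end of Day 44. Step 2 leaves some error when only month and year are known, but the imputed date can no longer leave the reported month. The one-day completer shift disappears only where EX supplies the date.

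The cost is a few sentences in the SAP, a small programming change and one listing, with no new data. The downside is slightly shorter TE time for a few subjects, so a small number of late events may be classed as post-treatment; they still appear in the AE listing.

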Appendix B: Imputation Rules for Missing Prior/Concomitant Medication Dates

Imputation rules for missing or partial medication start/stop dates are defined below:

1. Missing or partial medication start date:
 - a. If only DAY is missing, use the first day of the month.
 - b. If DAY and Month are both missing, use the first day of the year.
 - c. If DAY, Month and Year are all missing, use a date before the first dose date (to impute in practical, use the informed consent date).
2. Missing or partial medication stop date:
 - a. If only DAY is missing, use the last day of the month.
 - b. If DAY and Month are both missing, use the last day of the year.
 - c. If DAY, Month and year are all missing, assign ‘continuing’ status to stop date (in practical, use the End of Study Date to impute).

In summary, the prior, concomitant, or post categorization of a medication is described below.

Table 12-2 Prior, Concomitant, and Post Categorization of a Medication

Medication Start Date	Medication Stop Date			
	< First Dose Date of Run-in TE Period	≥ First Dose Date and < End Date of Run-in TE Period	≥ First Dose Date and ≤ End Date of Treatment TE Period	> End Date of Treatment TE Period
< First dose date of Run-in TE period	P	PC1	PC1C2	PC1C2A
≥ First dose date and < End date of Run-in TE Period	-	C1	C1C2	C1C2A
≥ First dose date and ≤ End date of Treatment TE Period	-	-	C2	C2A
> End date of Treatment TE Period	-	-	-	A

P: Prior; C1: Concomitant during the Run-in Period; C2: Concomitant during the Treatment Period; A: Post

Imputation rules for missing and/or partial dates of non-pharmacological treatment/procedure will follow the same imputation rule.

